#### 11.1.3 Presentation of Results

Parasitaemia data will be listed for all enrolled participants and summarised for the PD population. PD parameters will be presented for all participants included in the PD population.

Parasite life-stage data (pfs25, pfMGET and sbp1 qRT-PCR) will be listed by participant and timepoint.

A full report on the pharmacodynamic data analysis will be included in the appendices of the CSR. This report will include a listing of PD endpoints ( $PRR_{48}$ ,  $PCt_{1/2}$ ), a table for Summary of PD endpoints by dose group and a figure for individual log-parasitaemia regression fit.

List of planned tables, listings and figures are in Appendix, Table A.

## 11.2 PK Analysis

### Analysis Set: PK Analysis Set

PK endpoint: The pharmacokinetics of MMV367 calculated using non-compartmental methods.

#### 11.2.1 Data Handling

##### Imputation of Non-Numerical or Negative Values

The imputation of non-numerical or negative values reported in the input data set will be performed as follows:

- Pre-dose sample times will be entered as zero
- Values that are below the limit of quantification (BLQ) obtained prior to the  $C_{max}$  will be entered as zero
- Values that are BLQ after the  $C_{max}$  will be treated as missing.
- Should partial AUCs be required then values that are BLQ after  $C_{max}$  may be imputed as zero for these partial areas if lambda-z cannot be determined.
- Values that are quantifiable after at least 2 consecutive BLQ values after  $C_{max}$  will be treated as missing for the calculation of PK parameters.

##### Missing data

- Values that are reported as "No Result" or "No Sample" etc. will be treated as missing

#### 11.2.2 Rules for Pharmacokinetic Parameter Estimation using WinNonlin

Plasma concentration vs time profiles of MMV367 will be generated for each participant to allow for PK analysis. Pharmacokinetic parameters will be estimated using standard Phoenix WinNonlin methods, details of which may be found in the documentation accompanying the WinNonlin software package. The following constraints will apply:

Parameter Estimation	Constraint
Trapezoidal Method	Linear trapezoidal linear/log interpolation method
Number of Points used for Lambda-z	At least 3, not including $C_{max}$
Minimum Requirements for AUC	At least 3 consecutive quantifiable concentrations
Dose	Actual dose
Sampling Times	Actual sampling times

Where possible, the elimination rate constant (lambda-z) will be calculated for all participants. The value of lambda-z will be determined by the slope of the regression line of the natural log transformed concentrations vs time.

The choice of data points for determination of lambda-z will be applied by the Phoenix software as a default method, the pharmacokineticist who may adjust the selection to provide a more appropriate fit and records of this will be documented in the software data.

#### 11.2.3 Data Quality

The following flags/footnotes may be applied to the pharmacokinetic parameters:

Flag	Footnote
a	Rsq of regression was <0.8
b	Extrapolated portion of AUC 0-inf >20%
c	Insufficient post-C max data points for estimation of lambda-z
d	Entire profile BLQ, no pharmacokinetic parameters could be calculated
e	Regression could not be fitted

In the event that a reliable lambda-z cannot be determined, or the extrapolated portion of AUC0-inf is >20%, then the parameter estimates derived using lambda-z and/or AUC0-inf may be deemed unreliable and excluded from the summary statistics. Additional flags may be applied based on emerging data.

#### 11.2.4 PK parameters

The following pharmacokinetic parameters for MMV367 in plasma will be estimated where possible and appropriate for each participant and dose group:

CDISC Term	Parameter	Definition	DP or SF	No. of DP/SF
TMAX	T max	Time of maximum observed concentration	DP	2
CMAX	C max	Maximum observed concentration	SF	3
AUCLST	AUC last	Area under the curve from 0 time to the last measurable concentration	SF	3
AUCIFO	AUC 0-inf	Area under the curve from 0 time extrapolated to infinity	SF	3
LAMZHL	t 1/2	Apparent elimination half-life	DP	2
LAMZ	Lambda-z	Slope of the apparent elimination phase	DP	4
CLFO	CL/F	Total body clearance after extravascular administration	SF	3
VZFO	V z /F	Apparent volume of distribution based on the terminal phase after extravascular administration	SF	3

DP=decimal places

SF=significant figures

#### 11.2.5 Presentation of Results

All bioanalytical data will be listed and summarised according to the actual sampling timepoint.

If the actual sampling time is not within  $\pm 20\%$  of the scheduled sampling time, the concentration value at the sampling time point may be excluded from descriptive statistics and PK parameter estimation.

All pharmacokinetic parameters generated will be listed and summarised. Where pharmacokinetic data fails to meet the defined criteria in Section 11.2.3. (Data Quality) the affected results will be excluded from the descriptive statistics will be flagged as per exclusion reason.

#### **11.2.5.1. Bioanalytical and PK Parameters Listings**

All bioanalytical and pharmacokinetic data generated will be listed in individual tables according to the analyte and treatment.

#### **11.2.5.2. Bioanalytical and Pharmacokinetic Summary Tables**

Bioanalytical and PK parameters summary tables will be performed by SSR.

Summary statistics (i.e., mean, median, SD, CV%, minimum, maximum, n, geometric mean, geometric SD and geometric CV%) will be calculated for PK results for each time point, parameter and dose group.

All summary statistics (i.e., mean, median, SD, CV%, minimum, maximum and n) will be presented for all PK parameters by dose level. Also, geometric mean, geometric SD and geometric CV% will be presented for all PK parameters (except  $T_{max}$ ) by dose group. The  $T_{max}$  summary statistics will be provided as n, minimum, median, and maximum only.

Additional summary tables might be produced if required and requested.

#### **11.2.5.3. Bioanalytical and Pharmacokinetic Figures**

All arithmetical mean plasma concentration vs. time curves will be produced by dose group on both linear/linear and  $\log_{10}$ /linear scales.

All spaghetti plots of individual plasma concentrations against actual sampling times after dosing grouped by dose level will be produced on both a linear/linear and  $\log_{10}$ /linear scale. Each participant's concentration profile will be represented on these plots with a different symbol and a legend will be included on the plots to define the symbols used.

List of summary tables, listings and figures are in Appendix, Table A.

### **11.3 Safety**

Analysis Set: Safety data will use both FAS and IMP Sets

Endpoint: The incidence, severity and relationship to MMV367 and malaria challenge of adverse events.

Safety and tolerability will be assessed by clinical review of the following parameters:

- Adverse events (AEs)
- Vital signs
- 12-lead ECG
- Clinical Laboratory analysis
- Physical examination

#### **11.3.1. Adverse Events**

AEs will be reported according to the volunteer infection studies (VIS) plausible windows and reporting rules:

---

- Inoculum-emergent AEs (IEAEs)= AEs beginning any time from inoculation with the challenge agent until the end of study.
- Treatment-emergent AEs (TEAEs)= AEs beginning any time from administration of the IMP until the end of study.

Adverse Events of Special Interest (AESIs) may be serious or non-serious and are defined by the Sponsor as being of specific scientific and/or medical concern to the Sponsor's product or program. Evaluation on AESI will be based on both Safety Set and FAS depending on if it is treatment emergent or inoculum emergent adverse events.

Any abnormalities listed below should be reported as an AESI.

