4 STUDY DESIGN

4.1 OVERALL DESIGN

This is an open-label, adaptive study that will utilise the *P. falciparum* induced blood stage malaria (IBSM) model to characterise the pharmacokinetic/pharmacodynamic (PK/PD) profile and safety of MMV367 (the IMP). Up to 18 participants will be enrolled in cohorts of up to 6 participants each. The study will proceed as follows for all participants:

- Screening period of up to 28 days to recruit healthy adult volunteers.
- Day 0: Intravenous inoculation with approximately 2,800 viable *P. falciparum*-infected erythrocytes.
- Days 1-3: Daily follow up via phone call or text message.
- Days 4-7: Daily site visits for clinical evaluation and blood sampling to monitor malaria parasitaemia via quantitative polymerase chain reaction (qPCR).
- Day 7 PM: Start of confinement within the clinical trial unit.
- Day 8: Administration of a single oral dose of the IMP (MMV367). Different doses of MMV367 will be administered across and within cohorts in order to effectively characterise the PK/PD relationship (see Section 4.3 for dose selection rationale).
- Days 8-11: Regular clinical evaluation and blood sampling to monitor malaria parasitaemia and measure MMV367 plasma concentration.
- Day 11 AM: End of confinement within clinical trial unit.
- Days 12-23: Outpatient follow-up for clinical evaluation and blood sampling.
- Day 24: Initiation of compulsory definitive antimalarial treatment with Riamet® (artemether/lumefantrine) and/or other registered antimalarials if required (see section 6.1). Treatment will be initiated earlier than Day 24 in the event of:
 - Insufficient parasite clearance following IMP dosing (parasitaemia not reduced ≥ 10 -fold by Day 10 compared with peak parasitaemia on Day 8).
 - Parasite regrowth following IMP dosing (initial parasite clearance is followed by asexual parasite regrowth above 5000 parasites/mL).
 - Participant discontinuation/withdrawal (see Section 7),
 - Investigator's discretion in the interest of participant safety.
- Day 27: End of study visit for final clinical evaluation and to ensure complete clearance of malaria parasitaemia (at least one negative malaria PCR result required).

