4.3 JUSTIFICATION FOR DOSE

MMV367 will be administered as a single oral dose on Day 8, with different doses to be tested across and within cohorts to effectively characterise the PK/PD relationship. Participants will be randomised to a dose group on the day of dosing.

Rationale for highest dose

The highest dose of MMV367 administered in this study will be no more than 1500 mg. Testing of this dose may be required to determine the maximum parasite killing rate of MMV367. This dose was previously shown to be well tolerated by healthy volunteers and is equal to the maximum single dose of MMV367 administered in the FIH SAD study. There were no IMP-related AEs or SAEs recorded in the 1500 mg dose cohort (n=8, randomised 6 IMP: 2 placebo), and the incidence of all AEs was no higher than in lower dose cohorts. Additionally, PK data indicated that the mean group exposure following dosing with 1500 mg MMV367 did not exceed the exposure cap set for this FIH study. The exposure cap was 376

$\mu\text{g.h/mL}$ for AUC_{inf} and $23.8 \mu\text{g/mL}$ for C_{max} . Dosing with 1500 mg MMV367 in the FIH study was associated with a mean group exposure of $183 \mu\text{g.h/mL}$ for AUC_{inf} and $5.43 \mu\text{g/mL}$ for C_{max} . Thus, a safety margin exists in the event of higher exposure in the healthy participants with induced blood-stage malaria.

Dose selection for Cohort 1

The doses to be tested in Cohort 1 will be as follows:

MMV367 dose	20 mg	90 mg	1500 mg
Number of participants	3	2	1

Preclinical data indicates that MMV367 exhibits potent and fast acting activity against asexual blood stage *P. falciparum*. Preliminary modelling using human PK data generated in the FIH study combined with preclinical PD data (humanised mouse model of malaria) has allowed estimation of efficacious doses in humans with acute uncomplicated *P. falciparum* malaria.

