Parasite regrowth following initial parasite clearance is required to effectively characterise PK/PD parameters such as the half maximum effective concentration (EC_{50}) of MMV367. A single dose of 20 mg is expected to result in initial parasite clearance in the IBSM model (\log_{10} parasite reduction ratio over a 48 h period [PRR_{48}] median 2.9, 95% CI: 0.26 - 5.8), but subsequent parasite regrowth is expected to occur. It is predicted that parasitaemia will return to the pre-dose baseline with a median of 7 days post-dosing (95% CI: 2.5 - 14). Additionally, modelling indicates that there is a 50% chance for a typical individual dosed with 20 mg to have a full parasitaemia profile above the lower limit of quantification (LLOQ) of the qPCR assay. Thus, a significant amount of data is expected to be generated at this dose level and three participants will be dosed with 20 mg MMV367 in Cohort 1.

Testing of 90 mg MMV367 is considered important because it is predicted to represent an “intermediate” dose level. That is, modelling indicates that 90 mg will result in faster parasite clearance (\log_{10} PRR_{48} median 3.6, 95% CI: 1.8 – 6.2) compared with 20 mg for a typical individual, while retaining a good chance of parasite regrowth occurring and thus contributing to refining the MMV367 EC_{50} estimate. Two participants will receive 90 mg MMV367 in Cohort 1.

Testing of 1500 mg MMV367 is required to characterise the PK/PD parameters across the full dose range, in particular the maximum killing rate (E_{max}). The chance of parasite regrowth occurring at this dose level is considered very low and thus data from this dose level will have a long duration of observable maximum killing rate ensuring a reliable estimation of the maximum clearance rate (E_{max}), however it is not anticipated to contribute to refining the estimate of the EC_{50} . Therefore, one participant dosed with 1500 mg is considered sufficient in the first cohort.

Dose selection for Cohort 2

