6.1.2 DOSING AND ADMINISTRATION

IMP

A single oral dose of MMV367 will be administered on Day 8 after an overnight fast of ≥ 8 hours. The IMP will be administered as an oral suspension in sterile water. Specific dosing instructions will be documented in the pharmacy manual. Participants will be required to remain fasted for 4 hours after dosing. Different doses of MMV367 will be tested across and within cohorts.

The doses to be tested in Cohort 1 will be as follows:

MMV367 dose	20 mg	90 mg	1500 mg
Number of participants	3	2	1

Specific doses to be tested in subsequent cohorts will be decided by the SDRT based on emerging data during the study (safety, PK, and PD data from preceding cohorts). The maximum dose to be tested in the study will be no more than 1500 mg.

Challenge Agent

The malaria challenge agent, containing an estimated 2,800 viable *P. falciparum* 3D7 parasite-infected erythrocytes in a volume of 2 mL, will be administrated intravenously on Day 0. The actual number of parasites inoculated will take into account the loss of viability resulting from cryopreservation, storage and thawing. Participants will undergo intravenous cannulation. The inoculum will be injected, and the cannula flushed with clinical grade saline. The cannula will then be removed. An extra syringe will be prepared to quantify the parasite count of the challenge agent by PCR.

Definitive antimalarial medications

Compulsory definitive antimalarial treatment for all participants will be initiated on Day 24, if not initiated earlier in accordance with the criteria described in Section 4.1.

Riamet® tablets will be administered as six oral doses of four tablets (total course of 24 tablets equivalent to 480 mg artemether and 2.88 g lumefantrine). The second dose of four tablets will be administered 8±1 h after the first dose. The remaining doses will be administered twice daily (morning and evening).

Malarone® will be utilised as a backup medication to Riamet® in the event of allergy or contraindication to Riamet®. A treatment course consists of four tablets administered daily for three days (total course of 12 tablets equivalent to 3 g atovaquone and 1.2 g proguanil hydrochloride).

Participants may be treated with Primacin® at the Investigator's discretion to ensure clearance of gametocytes. If needed, participants will be administered a single oral dose of six Primacin® tablets (total dose 45 mg primaquine) with food.

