8.3.6 ADVERSE EVENT REPORTING

It is the Investigator's responsibility to document and report all AEs occurring in the clinical trial whether spontaneously reported by the participant, observed by the Investigator (either directly or by laboratory or other assessments), or elicited by general questioning. The period of observation for collection of AEs extends from the time of inoculation with the malaria challenge agent to EOS. These AEs must be recorded on specific AE pages of the eCRF. Events reported prior to this will be recorded as medical history, unless the symptoms worsen during the trial.

The following information should be recorded for all AEs:

- Description
- Dates and times of onset and resolution
- Seriousness (SAE or not)
- AESI (yes/no)
- Severity
 - If severity of an AE changes, only one AE will be reported, with the highest severity recorded in the eCRF and listings and tables. In the clinical file (source data), the description of the AE will report the various severities observed over time.
 - If the AE resolves and then reoccurs, then two AEs will be reported.
- Action taken in response to the AE (including treatment given).
- Outcome.
- Relationship to the trial treatments or procedures (causality assessment), including the IMP, malaria challenge agent, definitive antimalarial medications, or any other treatment or procedure conducted during the trial.

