#### 11.3.1.2.2. Tables

The number of events, as well as the number and percentage of participants experiencing an AE, will be summarised by, dose group and overall as follows:

Overall summary of IEAEs (FA set)  
Overall summary of TEAEs (IMP set)

Summary of IEAEs by System Organ Class and Preferred Term - All Causalities (FA set)  
Summary of TEAEs by System Organ Class and Preferred Term - All Causalities (IMP set)

Summary of IEAEs by System Organ Class, Preferred Term and Maximum Severity - All Causalities (FA set)

Summary of TEAEs by System Organ Class, Preferred Term and Maximum Severity - All Causalities (IMP set)

Summary of Malaria-Related IEAEs by System Organ Class and Preferred Term (FA set)  
Summary of IMP-Related TEAEs by System Organ Class and Preferred Term (IMP set)

Summary of Malaria-Related IEAEs by System Organ Class, Preferred Term and Maximum Severity (FA set)

Summary of IMP-Related TEAEs by System Organ Class, Preferred Term and Maximum Severity (IMP set)

Summary of IE SAEs by System Organ Class and Preferred Term - All Causalities (FA set)  
Summary of TE SAEs by System Organ Class and Preferred Term - All Causalities (IMP set)

Overall Summary of IE AESIs (FA set)  
Overall Summary of TE AESIs (IMP set)

Summary of IE AESIs by System Organ Class and Preferred Term - All Causalities (FA set)  
Summary of TE AESIs by System Organ Class and Preferred Term - All Causalities (IMP set)

Summary of IEAEs Leading to Study Discontinuation by System Organ Class and Preferred Term - All Causalities (FA set)

Summary of TEAEs Leading to Study Discontinuation by System Organ Class and Preferred Term - All Causalities (IMP set)

For the summary tables, participants who experience the same AE (in terms of the MedDRA preferred term) more than once will only be counted once.

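### The TEAE tables run to end of study with no split at definitive antimalarial treatment, whose timing is expected to depend on MMV367 dose

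*SAP*

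**What the plan says.** SAP 11.3.1 defines two windows, inoculum-emergent and treatment-emergent, and both close at end of study. The second is "Treatment-emergent AEs (TEAEs)= AEs beginning any time from administration of the IMP until the end of study". This matches the collection period in Protocol 8.3.6: "The period of observation for collection of AEs extends from the time of inoculation with the malaria challenge agent to EOS".

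Protocol 4.3 fixes the start of the TEAE window: "MMV367 will be administered as a single oral dose on Day 8". End of study is Day 27. Between the two, Protocol 6.1.2 says: "Compulsory definitive antimalarial treatment for all participants will be initiated on Day 24, if not initiated earlier". One trigger for earlier treatment in Protocol 4.1 is that "initial parasite clearance is followed by asexual parasite regrowth above 5000 parasites/mL"; another is a fall of less than 10-fold by Day 10.

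Protocol 4.3 links the regrowth trigger to dose. At 20 mg regrowth is expected, and it is predicted that "parasitaemia will return to the pre-dose baseline with a median of 7 days post-dosing" (95% CI 2.5 to 14). At 90 mg regrowth keeps a good chance, with no timing given. At 1500 mg its chance is put as very low.

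SAP 11.3.1.2.2 lists nine TEAE tables by dose group on the IMP set. Two are limited to IMP-related events and seven are not. SAP 11.3.1.1 and 11.3.1.2.1 put relationship to rescue medication in the listings only.

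**The concern.** The secondary endpoint is the incidence, severity and relationship to MMV367 of adverse events. A reader will compare the TEAE tables across dose columns. In those tables, an event on the first day after MMV367 and one that follows regrowth or a Riamet course count alike. How the 19 days divide between these situations is itself partly an outcome of the MMV367 dose.

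All-cause incidence by dose does get used. Protocol 4.3 supports the top dose partly by noting that overall AE incidence in the first-in-human 1500 mg cohort was no higher than at lower doses. The same reading here would mix tolerability of MMV367 with regrowth symptoms and with time after another drug. Protocol 8.3.4.2 asks investigators to distinguish, where possible, events due to the challenge agent, MMV367 and the definitive antimalarials. The planned tables summarise the first two attributions but not the third. With 3, 2 and 1 participants per dose in Cohort 1, a single event can change the picture.

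**Working it through.** **Inputs.** MMV367 on Day 8; routine definitive treatment on Day 24; end of study on Day 27 (Protocol 4.1). Predicted return to pre-dose parasitaemia at 20 mg: 7 days (2.5 to 14) (Protocol 4.3). Half-life about 17 h (Protocol 4.2). Five half-lives taken as 4 days (Protocol 5.1 and 8.3.9).

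**The protocol's own figure.** Dosing to Day 24 in half-lives: 16 × 24 / 17 = 22.6, against about 22 stated. It reproduces. Five half-lives are 5 × 17 / 24 = 3.5 days, which the protocol rounds up to 4.

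**Window.** 27 − 8 = 19 days.

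**Share of the window after definitive treatment starts** = (19 − days from dosing to treatment) / 19.

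| Case | Days to treatment | Days after | Share |
|---|---|---|---|
| 1500 mg, treated Day 24 | 16 | 3 | 3/19 = 16% |
| 20 mg, median | 7 | 12 | 12/19 = 63% |
| 20 mg, late limit | 14 | 5 | 5/19 = 26% |
| 20 mg, early limit | 2.5 | 16.5 | 16.5/19 = 87% |

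The 20 mg rows assume that treatment starts when parasitaemia returns to baseline. The actual trigger is 5000 parasites/mL. Protocol 4.2 expects the Day 8 count to exceed that level, so the trigger would be reached no later than the return to baseline. Detection then waits for the next PCR sample, which pushes the start later. No row can be filled for 90 mg.

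**What the share does not measure.** The Riamet course is six doses, the second at about 8 h and the rest twice daily, so it lasts about 60 h or 2.5 days. It fits nominally within the 3 days left after Day 24, so acute exposure is similar at every dose. At 20 mg, about 12 − 2.5 = 9.5 of the 12 days come after the course has ended.

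**Would a before-treatment column alone give a fair dose comparison?** Suppose a background rate of 0.05 AE per day at every dose and no drug effect (an assumed rate). The chance of at least one event is 1 − exp(−0.05 × days):
- before treatment, 20 mg (7 days): 30%
- before treatment, 1500 mg (16 days): 55%
- full window, any dose (19 days): 61%

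The unequal periods create a false rise with dose, which the equal 19-day window does not. Early treatment is also triggered by regrowth, so symptoms that begin during regrowth stay in the before-treatment column.

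**Would a 4-day window be free of definitive treatment?** Not entirely. The early limit of 2.5 days at 20 mg lies inside it, as does treatment for insufficient clearance by Day 10. If the predicted log10 PRR48 (20 mg: 2.9, 0.26 to 5.8; 90 mg: 3.6, 1.8 to 6.2) is read as a normal spread between individuals, SD = 5.54/3.92 = 1.41 and 4.4/3.92 = 1.12. P(below 1) is then about 9% at 20 mg and 1% at 90 mg. Such participants need a flag.

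**The case against.** The best defence is that the plan already answers the endpoint as worded. Relationship to MMV367 is part of it, and two TEAE tables by dose group are restricted to IMP-related events. Expected malaria symptoms are classed as challenge-agent-related (Protocol 8.3.4.2) and so appear in the malaria-related tables. An all-causality table includes other causes by design, and a window to end of study is a common convention that gives every dose the same nominal follow-up. Safety analysis is descriptive, at most 18 people are dosed, and the listings give onset, each causality judgement and rescue dates, so cases can be read one by one.

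Most of this stands. It means that the window itself is not an error. It does not fill the gap: the causality judgements are made open label, they cover the same window, and no table summarises events related to, or starting after, definitive treatment.

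A reader might infer from 63% against 16% that low-dose tables are four times as contaminated, or that low-dose groups collect regrowth and definitive-treatment events over most of the window. The documents do not support either. The figures are calendar days, everyone takes definitive treatment, and most of the extra days follow the end of the course. Participants already treated and PCR-negative may also skip Days 17, 20 and 24, which could reduce AE ascertainment in the early-treated and pull the other way.

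**Conclusion.** The point holds as a gap in presentation. The TEAE window contains compulsory definitive treatment for everyone, its start is expected to be earlier at low doses, and none of the nine TEAE tables separates or summarises events on that basis. On the stated proxy, about 12 of 19 days at 20 mg (5 to 16.5) and 3 of 19 at 1500 mg fall after treatment starts. The 20 mg figure is a model prediction, and nothing can be said for 90 mg or for doses in later cohorts.

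A reader might go further and conclude that the tables will hide or reverse a dose-related tolerability signal. That cannot be shown: the documents give no AE rates by period, the differences in ascertainment may offset part of any excess, and the groups are too small to predict a direction.

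**What to change.** Keep the to-end-of-study TEAE and IEAE tables. In SAP 11.3.1, 11.3.1.2.2 and Appendix Table B, add by dose group:

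- (a) AEs split by onset before versus on or after the first definitive antimalarial dose, with person-days at risk shown for each period;
- (b) a summary of AEs judged related to definitive treatment;
- (c) for descriptive dose comparison, TEAEs with onset in a fixed window of equal nominal length at every dose, for example the first 4 days after dosing (the protocol's own five half-lives), flagging any participant who starts definitive treatment within it.

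State that the before-treatment column is not to be used alone to compare doses, because its length depends on dose and it still contains regrowth symptoms.

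The cost is SAP wording, a period flag and a few more descriptive tables. Treatment dates (SAP 7.1 and 9) and AE onset times (SAP 11.3.1.1) are already collected, so no new data are needed and treatment does not change. The fixed window leaves later-onset events to the to-end-of-study tables, which is a reason to keep both.

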8.3 ADVERSE EVENTS AND SERIOUS ADVERSE EVENTS

8.3.1 DEFINITION OF ADVERSE EVENTS (AE)

An AE is any untoward medical occurrence, i.e., unfavourable and unintended sign (including an abnormal laboratory finding), symptom or disease that occurs in a participant during the course of the trial. An AE does not necessarily have a causal relationship with trial treatments or procedures.

AEs include, but are not limited to:

- A new symptom, sign or medical condition.
- A disease or medical condition detected or diagnosed during the course of the trial even though it may have been present prior to the start of the trial.
- An exacerbation of a pre-existing medical condition/disease.
- An increase in frequency or intensity of a pre-existing episodic disease or medical condition.
- Continuous persistent disease or symptoms present at trial start that worsen following the start of the trial.
- An abnormal assessment (e.g., change on physical examination, ECG finding) if it represents a clinically significant finding that was not present at trial start or worsened during the course of the trial.
- An abnormal laboratory test result if it represents a clinically significant finding (e.g., CTCAE grade 2 or above), symptomatic or not, which was not present at trial start or worsened during the course of the trial or led to dose reduction, interruption or permanent discontinuation of trial treatment.

Borderline abnormal laboratory findings and other objective assessments should NOT be routinely captured and reported as AEs. However, abnormal laboratory findings or other objective measurements that meet the following criteria should be captured and reported in the AE section of the eCRF:

- The result meets the criteria for reporting as an SAE.
- The test result is associated with accompanying symptoms, and/or
- It requires additional diagnostic testing or medical/surgical intervention, and/or
- It leads to a change in trial dosing, or discontinuation from the trial, significant additional concomitant drug treatment, or other therapy, and/or
- It is considered by the Investigator to be clinically significant or represent a clinically significant change from baseline.

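### An adverse event already ongoing at dosing that worsens after MMV367 is left out of every IMP-set adverse event output, because treatment-emergent is defined by onset alone

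*SAP*

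**What the plan says.** SAP section 11.3.1 sets two reporting windows, both defined by when the event starts. Inoculum-emergent AEs (IEAEs) are "AEs beginning any time from inoculation with the challenge agent until the end of study". Treatment-emergent AEs (TEAEs) are "AEs beginning any time from administration of the IMP until the end of study".

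Protocol section 8.3.6 says how an AE is recorded:
- On a change of grade: "If severity of an AE changes, only one AE will be reported, with the highest severity recorded in the eCRF and listings and tables".
- On the course of severity: "In the clinical file (source data), the description of the AE will report the various severities observed over time".
- On timing, the record holds "Dates and times of onset and resolution". SAP section 11.3.1.1 lists the same items for output and derives duration and onset relative to IMP. Neither document lists a date of grade change.
- On recurrence: "If the AE resolves and then reoccurs, then two AEs will be reported".

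In SAP section 11.3.1.2.2 and Appendix Table B, every AE table and listing on the IMP set is limited to treatment-emergent events. IMP-related tables exist only for TEAEs; the related-event tables for IEAEs concern malaria.

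**The concern.** MMV367 is given on Day 8 of an induced infection. Protocol section 7.1 expects that some participants may already have mild to moderate malaria signs and symptoms by then. Such an AE can be ongoing at dosing and become worse afterwards. Under the two rules together it remains a pre-dose event at its peak grade, so it counts as an IEAE and not as a TEAE.

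The incidence, severity and relationship to MMV367 of AEs form a secondary endpoint (Protocol section 3, SAP section 3.5.2.1). The IMP-set tables are the ones a reader will use to answer it. For this type of event they can err in one direction only, by understating incidence and maximum severity.

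The protocol does recognise worsening, but at a different baseline. Section 8.3.1 counts as an AE "Continuous persistent disease or symptoms present at trial start that worsen following the start of the trial", and section 8.3.6 makes a similar exception for events that precede inoculation. The SAP defines a treatment baseline as well as an inoculation baseline (section 4.2.2), yet no text applies the worsening principle at dosing.

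**Working it through.** The plan states no figure on this point, so there is none to reproduce. The check is to apply the two rules to cases, and then to bound the effect.

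**Step 1: apply the rules.** Inoculation is Day 0 and dosing is Day 8. An event is an IEAE if the onset on its record is at or after inoculation, and a TEAE if that onset is at or after dosing.

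| Case | Records | Onset used | IEAE | TEAE |
|---|---|---|---|---|
| A. Headache from Day 7 at Grade 1, continuous, Grade 3 on Day 9 | 1 | Day 7 | yes | no |
| B. Headache from Day 7, resolves before dosing, returns on Day 9 | 2 | Day 9 (second record) | yes | yes |
| C. New headache on Day 9 | 1 | Day 9 | yes | yes |

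If case C is also Grade 3, cases A and C have the same grade on the same day after the same drug, but only C reaches the IMP-set tables. In case A the investigator's judgement on MMV367 makes no difference, because the IMP-related tables select TEAEs before they look at causality.

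**Step 2: find where case A does appear.**
- FAS tables of IEAEs by dose group, including maximum severity, SAEs and AESIs (SAP section 11.3.1.2.2).
- The AE listing, with severity, relationship to IMP and onset relative to IMP (SAP sections 11.3.1.1 and 11.3.1.2.1).
- For symptoms in the malaria clinical score, the tabulation by symptom, dose group and time point (SAP section 11.3.8). These scores match CTCAE grades 1 to 3 (Protocol section 8.2.4) but carry no causality.
- For laboratory, vital sign and ECG values, the summaries of change from treatment baseline (SAP sections 11.3.3, 11.3.4 and 11.3.7).

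The AE outputs among these show the peak grade without its date, so they cannot place the peak before or after dosing.

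**Step 3: bound the effect of one such participant.** SAP section 11.3.1.2.2 counts a participant once per preferred term. The change in a row is 1/n if the participant is not otherwise in that row, and 0 if they are.
- Overall, with the maximum of 18 dosed (Protocol section 9.2): 1/18 = 5.6 percentage points. If enrolment stops after two full cohorts: 1/12 = 8.3 points.
- Cohort 1 dose groups of 3, 2 and 1 (Protocol section 4.3): 1/3 = 33.3, 1/2 = 50 and 1/1 = 100 points. These shrink if the same dose is repeated in a later cohort.

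**Step 4: scale under an assumption.** Let p be the share of dosed participants with an AE ongoing at dosing that later worsens. The documents give no value for p, so a range is shown. With 18 dosed, the expected number is 18p and the chance of at least one is 1 − (1 − p)^18.

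| Assumed p | Expected number | Chance of at least one |
|---|---|---|
| 5% | 0.9 | 0.60 |
| 10% | 1.8 | 0.85 |
| 20% | 3.6 | 0.98 |
| 30% | 5.4 | 0.998 |

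**The case against.** There are four arguments on the other side.

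*The events are reported anyway.* A reader might infer that they vanish from the study report. They do not: every dosed participant is in the FAS, and the outputs in Step 2 still hold them. With at most 18 dosed, a careful reader of the listing could pick out an event with pre-dose onset that was judged related to MMV367. This stands, and it limits the harm. It does not mend the IMP-set tables, and the listing still lacks the date of the peak.

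*Laboratory events are mostly unaffected.* A reader might extend the point to a Grade 1 ALT rise or neutropenia before dosing. Protocol section 8.3.1 says that borderline laboratory findings are not routinely AEs and gives Grade 2 or above as its example of clinical significance. A mild pre-dose value would usually not be recorded as an AE, and a marked rise after dosing would then have a post-dose onset and count as a TEAE. This stands, so the gap mainly concerns continuing symptoms.

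*The pre-dose onset is an inference.* Protocol section 8.3.6 does not say in so many words that a worsened event keeps its pre-dose onset. The SAP refers to reporting rules for volunteer infection studies, and the protocol to eCRF completion guidelines; neither is reproduced in these documents. That is fair, but a single record with one onset and no field for worsening leaves no other natural reading.

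*A worsening clause blurs challenge and drug effects.* Some progression of malaria would be counted as treatment-emergent. This carries little weight: new malaria symptoms after dosing already count as TEAEs, and causality to the challenge agent and to MMV367 is recorded separately.

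**Conclusion.** The point holds as a gap in the definition. An AE that continues through dosing and worsens afterwards is excluded from all IMP-set AE tables and listings, whatever its causality, and neither document closes the gap elsewhere. The conclusion assumes that the single record carries the pre-dose onset. It does not cover events that resolve and recur, which get a second record.

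The size is unknown, and two stronger readings are not supported. A reader might take 5.6 points as the least that each omitted event can cost. With 18 dosed it is the most that one participant can change an overall rate, and the change is zero where that participant already counts in the row. A reader might also suppose that events spanning dosing are the usual pattern. Protocol section 7.1 says only that some participants may have symptoms before Day 8, and sections 2.2.1 and 4.2 allow for none.

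The change is still worth making. It is cheap, it affects a secondary endpoint, and the dose groups are small enough for one participant to alter a row visibly.

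**What to change.** 1. In SAP section 11.3.1, define a TEAE as an AE that at or after IMP administration either begins, rises in CTCAE grade, becomes serious or meets an AESI criterion.
2. For AEs ongoing at dosing, capture from source the grade at dosing and the date and time of any later rise. For these events, capture also the date on which the event became serious or met an AESI criterion, if that came after dosing. The course of severity is already kept in source, so no new assessment of participants is needed. Keep the single record that Protocol section 8.3.6 requires.
3. Leave the IEAE definition and its tables as they are.

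The cost is a revised SAP definition, made before database lock, and one or two added eCRF items in a database that is already designed. Opening a new record at worsening would also work, but it contradicts Protocol section 8.3.6 and would need an amendment with ethics committee approval, so the single-record route is lighter. The downside is that some malaria-driven worsening enters the all-causality TEAE counts; the separate causality fields and the IMP-related tables keep it distinguishable.
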